3.2.2.2 LTE Period, MAD+LTE Period, and Active Treatment Period

The following analysis groups will be used for the LTE Period, MAD+LTE Period, and Active Treatment Period unless otherwise indicated. In case of very few subjects in any group, the analysis groups may be further pooled.

- Late Start A+B+C: MAD Cohorts A, B and C placebo-treated patients
- Late Start D: MAD Cohort D placebo-treated patients
- Early Start A: MAD Cohort A ISIS 814907-treated patients
- Early Start B: MAD Cohort B ISIS 814907-treated patients
- Early Start C: MAD Cohort C ISIS 814907-treated patients

- Early Start D: MAD Cohort D ISIS 814907-treated patients
- ISIS 814907 60 mg Q12W (LTE Period and Active Treatment Period):
 - LTE Period: All MAD Cohort A, B, and C roll-over subjects, regardless of randomization assignment. This group will be included for select analyses only in the LTE Period, e.g., AE and SAEs, safety analyses (except shift analyses for laboratory assessments), selected exploratory analyses only (including MRI volumetric, PET and clinical evaluations), PD and PK analyses.
 - Active Treatment Period: All MAD Cohort A, B, and C subjects, regardless of either randomization assignment or LTE enrollment status. This group will be included for select analyses only in the Active Treatment Period, e.g., serious TEAEs potentially related to Study Drug, overall summary of TEAEs, and safety MRIs.
- All Roll-over (LTE Period only, excluding PK analyses): All MAD Cohorts ISIS 814907-treated and placebo-treated roll-over patients.
- ISIS 814907 115 mg Q12W (LTE Period and Active Treatment Period): All MAD
 Cohort D roll-over subjects, regardless of randomization assignment (LTE Period). All
 MAD Cohort D subjects, regardless of either randomization assignment or LTE
 enrollment status (Active Treatment Period).
- Total Active (Active Treatment Period only, excluding PK analyses): All patients who receive at least 1 dose of ISIS 814907 in either the MAD or LTE periods.

In general, Early Start corresponds to a randomization assignment of active ISIS 804907 treatment in the MAD, whereas Late Start corresponds to a randomization assignment of Placebo in the MAD. The subjects and data which contribute to the analysis for a given population will be uniquely determined by both the Analysis period and Analysis group. For example, Early Start in the LTE Period includes data from subjects in the population randomized to active treatment during MAD who also enroll in the LTE; however Early Start in the MAD+LTE Period includes data from subjects in the population randomized to active treatment during MAD regardless of enrollment in the LTE.

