Cohort D: N = 16, mild AD, 90 mg ISIS 814907 or placebo x 4 doses *or* 115 mg ISIS 814907 x 2 doses

The overall randomization ratio in each cohort is 3:1 ISIS 814907 to placebo.

Following the 3-month Treatment Evaluation Period, there will be a 6-month Post-Treatment Period.

3.1.2 Long-Term Extension, Part 2

The open-label LTE, Part 2, of the study will start with Cohort C and allow all patients in Cohorts C and D to seamlessly transition from Part 1 to Part 2. This means that for Cohorts C and D patients Day 253 in Part 1 will correspond to Day -1 in Part 2. In Part 2, the Treatment Evaluation Period of 48 weeks will be followed by a Post-Treatment Period of 16 weeks.

All patients will receive ISIS 814907 in Part 2 and will be dosed at an 84-day interval, regardless of the dose interval utilized in Part 1. Cohort C patients will continue the Cohort C dose with a quarterly (84-day) dose interval in the LTE, Part 2; Cohort D patients will continue the Cohort D dose with a quarterly (84-day) dose interval in the LTE, Part 2. Cohort A and B patients who have completed the Treatment Evaluation and Post-Treatment Periods in Part 1 are also eligible to enter Part 2 of the study. For Cohorts A and B patients there will be a variable gap of time between the end of Part 1 and entry into Part 2. There is no prescribed minimum or maximum interval of time required before Cohort A and B patients completing Part 1 can enter Part 2 of the study, however all Cohort A and B patients participating in the LTE, Part 2, should be enrolled in Part 2 prior to the last patient in Cohort D entering Part 2 of the study. Patients who participated in Cohorts A and B will be able to start the LTE, Part 2 of the study at the Cohort C dose with a quarterly (84-day) dose interval, if permitted by the FSMG review of the Cohort C package for the dose-escalation meeting to Cohort D (2/3 of patients in Cohort C having received all doses of Study Drug in Part 1). Patients entering the LTE Part 2 will be maintained on the dose they received when they initiated Part 2. Dose levels and dosing regimen in the LTE, Part 2 could be adjusted in individuals or for the entire study based on ongoing review of the safety, PK/PD

profile by the FSMG and the Sponsor. In the LTE, Part 2, the Treatment Evaluation Period of 48 weeks will be followed by a Post-Treatment Period of 16 weeks.

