3.3 Number of Patients

Approximately 44 patients are planned to be randomized in this study. The number of patients randomized may be higher if some patients need to be replaced, the sizes of the cohorts are expanded to obtain further experience with particular dose levels and/or additional cohorts are added. A maximum of 64 patients may be randomized.

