10.2 Sample Size Considerations

While there is no statistical rationale for the sample size, it has been selected based on prior experience with generation 2.0 ASOs given by IT bolus injection to ensure that the safety, tolerability, PK, and exploratory PD will be adequately assessed while minimizing unnecessary patient exposure.

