10.6.4 Pharmacodynamic and Exploratory Analysis

The PD and exploratory analyses, including evaluation of target engagement, will be conducted on the Per-Protocol and Safety Populations.

The key analysis in the MAD, Part 1, of the study is the correlation of CSF trough concentration of ISIS 814907 on Day 85 with change in CSF tau concentration from baseline to final CSF collection. ISIS 814907 dose and PK (CSF trough concentration of ISIS 814907 on Day 85) will be related to target engagement using the change in CSF total tau level from baseline to Day 85 and to each CSF collection in the Post-Treatment Period. In the LTE, Part 2, of the study a key analysis will be the correlation of CSF trough concentrations of ISIS 814907 on Day 337 with change in CSF tau concentration from baseline to final CSF collection. Additional correlations between ISIS 814907 dose or PK (CSF trough concentration of ISIS 814907 on Day 85) and changes in PD endpoints may be produced.

Exploratory evaluations (Section 10.1.3) will be summarized using descriptive statistics by study visit and treatment group. Change and percent change from baseline over time will be summarized as appropriate. Placebo-treated patients will be pooled for analysis. Evaluations of biomarker and clinical evaluations may include dose- and PK-dependent effects and comparisons between patients receiving ISIS 814907 and those receiving placebo. Comparison between ISIS 814907 group and the pooled placebo may be performed in an exploratory manner. In addition, comparison between patients treated with ISIS 814907 from the start of Part 1 vs. placebo patients who only started ISIS 814907 in Part 2 of the study will be investigated to better understand the impact of delayed treatment. The impact of reported genetic modifiers of disease phenotype on study endpoints may be investigated.

Details will be described in the SAP.

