1.1 Study Overview

This is a Phase 1, multi-center, double-blind, randomized, placebo-controlled study of multiple IT bolus administrations of ISIS 814907 in patients with mild Alzheimer's Disease (AD) aged 50-74 years, inclusive.

This study is divided into 2 parts:

- Part 1: a randomized, double-blind, placebo-controlled multiple ascending dose (MAD) part, comprising a Screening Period of 8 weeks, a Treatment Evaluation Period of 13 weeks, and a Post-Treatment Period of 23 weeks
- Part 2: an open-label, long-term extension (LTE) part, comprising a Registration Period of 3 weeks (only for those who cannot transition seamlessly, i.e., patients from Cohorts A and B), a Treatment Evaluation Period of 48 weeks, and a Post-Treatment Period of 16 weeks (except in the UK (Amendment 7) where the Post-Treatment Period is 23 weeks)
 - o For patients participating in Cohorts A and B there will be a variable gap of time between the end of Part 1 and entry into Part 2
 - Patients participating in Cohorts C and D will seamlessly transition from Part 1 to Part 2. Day 253 in Part 1 (i.e., last visit of Part 1 Post-Treatment Period) will correspond to Day -1 in Part 2 (i.e., first visit of Part 2 Treatment Evaluation Period).

Multiple Ascending Dose, Part 1

Four (4) ascending dose level cohorts (A, B, C, and D) of patients were enrolled sequentially and randomized with an overall ratio of 3:1 to receive ISIS 814907 or placebo. A sentinel dosing strategy was implemented. The first 2 patients at a given dose level were assigned 1:1 active: placebo, and at least 1 week elapsed between initiation of treatment in these 2 patients and initiation of treatment in additional patients at this dose level. The remaining patients were assigned to active or placebo at a 5:1 ratio for cohorts with N = 8, 8:2 ratio for cohorts with N = 12, or 11:3 ratio for cohorts with N = 16 to ensure a 3:1 active: placebo balance in each cohort. Based on the profile of effects observed in non-human primate toxicology studies, 24 hours is expected to be a sufficiently long observation period to identify possible safety

issues. Thus, as a safety measure, the sentinel dosing algorithm utilized for this study required that 1-week elapsed between initiation of treatment in the first 2 patients and initiation of treatment in subsequent patients in the cohort. Identified and potential risks associated with ISIS 814907 are described in detail in the Investigator's Brochure.

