3. ANALYTICAL PLAN

3.1 General Overview of Analyses

Descriptive summary statistics including number of patients, mean, median, standard deviation, standard error of mean, interquartile range (25th percentile, 75th percentile), and range (minimum, maximum) for continuous variables, and counts and percentages for categorical variables will be used to summarize most data. Where appropriate, p-values will be reported. All

statistical tests will be conducted using 2-sided tests with 5% Type I error rate unless otherwise stated.

PK parameters will be summarized by treatment group including number of patients, mean, standard deviation, coefficient of variation (CV), geometric mean, median, minimum, and maximum.

All eCRF data and data transfers from external vendors (e.g., laboratory, cognitive and neuropsychiatric testing) will be provided in the subject data listings. Patient data listings will be presented for all patients enrolled into the study.

Within this document, the terms 'patient' and 'subject' are both used to describe the individual who enrolls in this study. The terms 'MAD' and 'Part 1' may be used interchangeably. Similarly, the terms 'LTE' and 'Part 2' may be used interchangeably.

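### The pooled Late Start A+B+C column in the MAD+LTE summaries mixes patients with and without a gap before the LTE, so it is not time-matched to any early-start column

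*Combined protocol and SAP*

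**What the plan says.** Protocol 10.6.4 says there will be a "comparison between patients treated with ISIS 814907 from the start of Part 1 vs. placebo patients who only started ISIS 814907 in Part 2", to understand the impact of delayed treatment, and leaves the details to the SAP. The SAP rules that bear on it are these:

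- **Groups (SAP 3.2.2.2 and Table B2).** Early starters appear as four separate columns, A, B, C and D. Late starters appear as two: Late Start D, and "Late Start A+B+C: MAD Cohorts A, B and C placebo-treated patients".
- **Baseline (SAP 3.2.3.1).** MAD+LTE changes are taken from the value before the first MAD dose.
- **Time axis (SAP 3.2.4).** By-visit summaries use the visit label in the data.
- **Gap (protocol 3.1.2).** "There is no prescribed minimum or maximum interval of time required before Cohort A and B patients completing Part 1" can enter Part 2. The same sentence adds that they should be enrolled before the last Cohort D patient enters, and SAP 1.1 repeats this. Cohorts C and D move across with no gap.
- **Gap reporting (SAP 3.5.2).** The time between the two parts is summarised by analysis group. It is not used to align or adjust anything.

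MAD+LTE output for MMSE, RBANS, CDR, MRI and CSF biomarkers is descriptive (SAP 3.7.1 to 3.7.3).

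**The concern.** Together, the pre-MAD baseline, the visit-label axis and the pooling put different elapsed times under one label within one column. For a Cohort A or B patient, any decline during the gap falls inside the change from baseline; a Cohort C patient has no such interval.

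The display matters because MAD+LTE is the natural place to read the delayed-treatment comparison. In the LTE Period, late starters are re-baselined before the LTE while early starters keep the MAD baseline (SAP 3.2.3.2), so the two are not on a common footing there. In MAD+LTE they share a baseline, but the main late-start column does not share a time scale with the columns beside it. A difference produced by elapsed time could be read as an effect of starting late.

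**Working it through.** **Planned group sizes.** Protocol 3.3: "Approximately 44 patients are planned to be randomized in this study". SAP 1.1 gives a sentinel pair of one active and one placebo patient per cohort, then "5:1 ratio for cohorts with N = 8, 8:2 ratio for cohorts with N = 12", and 11:3 for Cohort D.

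- Cohorts A and B, each: 1 + 5 = 6 active, 1 + 1 = 2 placebo
- Cohort C: 1 + 8 = 9 active, 1 + 2 = 3 placebo
- Cohort D: 1 + 11 = 12 active, 1 + 3 = 4 placebo
- Total: 33 + 11 = 44, which reproduces the plan's figure

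Late Start A+B+C is therefore 2 + 2 + 3 = 7, of whom 4 (57%) come from the gap cohorts. The group defined as "Early Start C: MAD Cohort C ISIS 814907-treated patients" has 9, none with a gap. These are planned numbers and assume full roll-over.

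**Elapsed time.** For Cohort C, MAD Day 253 is LTE Day -1. There is no Day 0, so LTE Day d falls 252 + d days after MAD Day 1. At LTE Day 449 this is 252 + 449 = 701 days. For Cohorts A and B it is 701 + g, where g is the gap.

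Mean elapsed time at Day 449, if A and B have the same mean gap in both arms:

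- Early Start C: 701
- Late Start A+B+C: 701 + (4/7)g
- Early Start A or B: 701 + g

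The pooled column is thus (4/7)g later than Early Start C and (3/7)g earlier than Early Start A or B.

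**Size.** Neither g nor a decline rate is in the documents. Assume linear decline of 1 to 3 points a year on a clinical scale. Offset in points = fraction × g / 365.25 × rate.

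| Assumed mean gap (days) | 4/7 × gap (share of 701) | Looks too bad beside Early Start C | 3/7 × gap | Looks too good beside Early Start A or B |
|---|---|---|---|---|
| 90 | 51 days (7%) | 0.14 to 0.42 | 39 days | 0.11 to 0.32 |
| 180 | 103 days (15%) | 0.28 to 0.84 | 77 days | 0.21 to 0.63 |
| 365 | 209 days (30%) | 0.57 to 1.71 | 156 days | 0.43 to 1.28 |

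**Are such gaps possible?** Cohorts A and B can enter the LTE only after the safety group has reviewed Cohort C. A cohort cycle takes at least about 7 days (sentinel lag) + 91 days (to Day 92) = 98 days. With instantaneous enrolment and review:

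- The LTE opens to A and B at 3 × 98 = 294 days after the first Cohort A dose.
- The last Cohort D patient enters at about 294 + 7 + 253 = 554 days.
- Cohort A patients finish Part 1 at about day 253 to 260, giving gaps of 34 to 301 days.
- Cohort B patients start 98 days later, giving gaps of 0 to 203 days.

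If each cohort instead takes 90 days to enrol (assumption), the ranges become 131 to 564 days for A and 0 to 406 days for B.

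**Precision of a split.** The SE of a difference in means is SD × √(1/n₁ + 1/n₂). For 7 against 9 it is 0.504 SD; for 3 against 9 it is 0.667 SD. The variance ratio is (0.667/0.504)² = 1.75.

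**The case against.** The strongest reply is that randomisation within cohort balances the gap. Cohorts A and B supply 12 of 21 active patients in A+B+C and 4 of 7 placebo patients, both 57%. With Cohort D included the shares are 12/33 and 4/11, both 36%. If mean gap and roll-over are equal by arm, all early starters against all late starters have the same expected elapsed time, and protocol 10.6.4 is not limited to Cohort C. This is correct, but Table B2 contains no pooled early-start column for MAD+LTE. The SAP allows further pooling if groups are very small, but does not plan it. As tabulated, a pooled late column stands beside separate early ones.

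Second, there is mitigation. Cohorts A and B have MMSE, RBANS, CDR and MRI at the Registration visit (protocol Appendix A.4), and SAP 3.7.3.5 shows CDR there under MAD+LTE, so decline up to LTE entry is partly visible. The gap itself is summarised. But that summary uses the same pooled group, so it averages A and B with C. SAP 3.5.2 also defines MAD+LTE time on study as the two segments added together, which omits the gap that change from baseline includes.

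Third, Late Start C alone would have 3 patients. That stands as a cost of the split; it does not justify mixing time scales under one label.

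A reader might also infer more than the documents support:

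- *That the gap is unlimited.* It has no per-patient maximum, but it has a calendar end at the last Cohort D patient's entry.
- *That a planned test is biased.* SAP 3.1 says "statistical tests will be conducted using 2-sided tests with 5% Type I error rate", but no test of Late Start A+B+C against Early Start C, or against any early group, is specified for MAD+LTE. Protocol 10.2 opens "While there is no statistical rationale for the sample size", so no power claim is at stake.
- *That the error always favours early treatment.* It reverses against Early Start A or B.
- *That PET is affected.* Cohorts A and B have no MAD PET (SAP 3.7.2.3) and missing values are not imputed (SAP 3.4.2), so change in this column can come only from Cohort C.

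**Conclusion.** The concern holds as a defect in a descriptive display. The misalignment follows from the SAP's own rules and needs no assumption beyond a non-zero gap in Cohorts A and B. Its direction depends on which early column is read: against late start beside Early Start C, in its favour beside Early Start A or B. Early Start D against Late Start D is unaffected, because neither has a gap.

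The size is not established. The range of about 0.14 to 1.7 points against Early Start C rests on assumed mean gaps of 90 to 365 days and assumed linear decline of 1 to 3 points a year. The Cohort B gap could be near zero, which would shrink it. The 3/7 figure also assumes that A and B have similar gaps, although A is likely to wait longer. No size or sign is offered for CSF biomarkers, where drug effect and untreated time act together.

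**What to change.** For the MAD+LTE summaries of MMSE, RBANS, CDR, MRI and CSF biomarkers (not PET):

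1. Show Late Start A+B and Late Start C as separate columns, with Late Start C beside Early Start C and Late Start A+B beside Early Start A and B.
2. Summarise the gap in SAP 3.5.2 by these split groups.
3. Plot values and change against actual time from first MAD dose. This also shows any difference in gap between A and B that a joint A+B column still hides.
4. Keep the pooled column, with a footnote that elapsed time at a given LTE label differs between its members.
5. Do not annualise CSF biomarker changes: dividing a drug-driven change by years that include an untreated gap would shrink it in A and B and add a new distortion.

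The cost is SAP wording, table shells and one derived time variable, with no new data and no change in conduct. The downside is small groups: about 4 and 3 patients, with the SE against Early Start C rising from 0.50 to 0.67 SD. That is why the pooled column should stay.

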3.2.1 Analysis Periods

There are four periods which will be used for analysis and are defined as:

- MAD Period: Analyses include data from MAD, Part 1.
- LTE Period: Analyses include data from LTE, Part 2.
- MAD+LTE Period: Analyses include integrated data from both MAD, Part 1 and LTE, Part 2, regardless of a subject's randomization assignment or LTE enrollment status. For example, a subject receiving MAD placebo treatment who does not enroll in LTE will still contribute data from the MAD to this analysis.
- Active Treatment Period: Analyses include data from study periods in which a subject receives active ISIS 814907 treatment. (Note: Study periods refer to Part 1 and/or Part 2, including post-treatment follow-up but excluding any variable gaps in time between Part 1 and Part 2 for subjects in Cohorts A and B). Data collected during a placebo dosing period are not included (except relevant baseline data). Subjects who receive MAD active treatment will contribute data regardless of LTE enrollment status. Subjects who receive MAD placebo treatment will only contribute data if enrolled and dosed in the LTE.

In general, listings will be created for the MAD Period and the MAD+LTE Period.

Safety, pharmacodynamic and exploratory analyses will be conducted for the MAD Period and the LTE Period separately.

The MAD+LTE Period will be used to analyze select biomarkers, neuroimaging and key clinical assessments:

- o MRI (exploratory)
- o Tau-PET/FDG-PET
- o CSF biomarkers including but not limited to total tau, phospho-tau and A-beta42
- o MMSE
- o RBANS
- o CDR

The Active Treatment Period will be used to analyze select safety endpoints including:

- Laboratory assessments: Potential clinically significant laboratory abnormalities, hepatotoxicity, and shift analyses
- o CSF Safety Panel
- o Safety MRIs
- o Incidence rates for treatment emergent adverse events (TEAEs) and serious TEAEs

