3.2.2 Analysis Groups

The analysis groups are described below according to the analysis periods in which they will be used.

3.2.2.1 *MAD Period*

- Pooled Placebo (excluding PK analyses): Cohorts A, B, C and D placebo-treated patients
- ISIS 814907 10mg Q4W: 10 mg ISIS 814907-treated patients
- ISIS 814907 30mg Q4W: 30 mg ISIS 814907-treated patients
- ISIS 814907 60mg Q4W: 60 mg ISIS 814907-treated patients
- ISIS 814907 115mg Q12W: 115 mg ISIS 814907-treated patients
- Total Active ISIS 814907 (excluding PK analyses): Cohorts A, B, C and D
 ISIS 814907-treated patients

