3.5.2 Time on Study Analysis

The time on study analysis described below will be included in the final analysis only.

Time on study (years) will be summarized by analysis group for the MAD, LTE, MAD+LTE and Active Treatment Periods using descriptive statistics. Total time on study (patient-years) in each analysis group will be included in the summaries.

Additionally for the MAD+LTE Period, time from last dose date in MAD to first dose date in LTE (years), and time from last study visit date in MAD to first dose in LTE (days and years, separately) will be summarized by analysis group using descriptive statistics.

Time on study (days) for each subject is defined as:

- MAD Period, LTE Period separately: last study visit date within the Period first dose date within the Period + 1
- Active Treatment Period, early starters: (last study visit date in MAD first dose date in MAD + 1) + (last study visit date in LTE first dose date in LTE + 1). For subjects not enrolled in LTE then it is the same as the MAD Period time on study.
- Active Treatment Period, late starters: last study visit date in LTE first dose date in LTE + 1.
- MAD+LTE Period: (last study visit date in MAD first dose date in MAD + 1) + (last study visit date in LTE first dose date in LTE + 1). For subjects not enrolled in LTE then it is the same as the MAD Period time on study.

Time on study (years) for each subject is calculated as the time on study (days) divided by 365.25. Total time on study (patient-years) is calculated as the sum of time on study (years) across subjects within the analysis group and period.

For the MAD+LTE Period: Time from last dose date in MAD to first dose date in LTE (years) is defined as: (first dose date in LTE – last dose date in MAD + 1)/365.25. Time from last study visit date in MAD to first dose in LTE (days) is defined as: first dose in LTE – last study visit

date in MAD + 1; Time from last study visit date in MAD to first dose in LTE (years) is: (first dose in LTE – last study visit date in MAD + 1)/365.25.

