3.5.3 Adverse Events

3.5.3.1 MAD Period and LTE Period

The incidence (proportion) of treatment-emergent adverse events (TEAEs) will be summarized for the MAD and LTE Periods separately, and incidence (rates) of TEAEs will be summarized for the Active Treatment period where indicated by *. The Medical Dictionary for Regulatory Activities (MedDRA) version 20.0 will be used. Summaries will be presented by preferred term (PT) and system organ class (SOC), unless otherwise indicated, for:

- Any TEAE* (summarized by PT only and by both SOC and PT)
- TEAEs potentially related to Study Drug. Related is defined as "Related", "Possible", or missing relationship to study drug, as determined by the investigator
- TEAEs potentially related to Lumbar Puncture (LP) procedure. Related is defined as "Related", "Possible", or missing relationship to LP procedure
- Any TEAE by severity*. At each level of subject summarization, a subject is classified according to the highest severity if the subject reported one or more events. TEAEs with missing severity will be categorized as "Missing" for this summary
- TEAEs potentially related to Study Drug by severity
- TEAEs potentially related to LP procedure by severity
- Serious TEAEs* (by PT only and by both SOC and PT)
- Serious TEAEs potentially related to Study Drug*
- Serious TEAEs potentially related to LP procedure*
- TEAEs leading to permanent study drug discontinuation* (by PT only and by both SOC and PT)

The number and proportion of LPs leading to TEAEs will be summarized for the MAD and LTE Periods separately. The severity of AEs and SAEs will be graded based on criteria from the Common Terminology Criteria for Adverse Events (CTCAE) Version 4.03, June 2010. SAEs and non-serious AEs that lead to permanent study drug discontinuation will be listed separately. Non-treatment emergent adverse event will be flagged in the data listing.

An adverse event will be regarded as treatment emergent if it is present prior to receiving the first dose of study drug (MAD: ISIS 814907 or placebo; LTE and Active Treatment Periods: ISIS 814907) and subsequently worsened, or is not present prior to receiving the first dose of

study drug (MAD: ISIS 814907 or placebo; LTE and Active Treatment Periods: ISIS 814907) but subsequently appeared.

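### The Active Treatment Period column labelled 60 mg Q12W also holds Part 1 data at 10, 30 and 60 mg Q4W (29.7% of planned person-time), and Table B3 has no such column

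*Combined protocol and SAP*

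**What the plan says.** SAP 3.2.2.2 uses the name ISIS 814907 60 mg Q12W in two analysis periods, with different membership.

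- **LTE Period:** Cohort A, B and C patients who rolled over. Only Part 2 data count, so the label is correct.
- **Active Treatment Period:** "Active Treatment Period: All MAD Cohort A, B, and C subjects, regardless of either randomization assignment or LTE enrollment status". The listed uses are select analyses, for example related serious TEAEs, the overall TEAE summary and safety MRI.

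SAP 3.2.1 says of the Active Treatment Period that "Subjects who receive MAD active treatment will contribute data regardless of LTE enrollment status". Part 1 placebo patients contribute only if they are dosed in Part 2. SAP 3.2.2.2 adds that the contributing subjects and data "will be uniquely determined by both the Analysis period and Analysis group".

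For time on study, SAP 3.5.2 adds Part 1 and Part 2 time for early starters (the entry beginning "Active Treatment Period, early starters: (last study visit date in MAD"). SAP 3.5.3.1 states that "incidence (rates) of TEAEs will be summarized for the Active Treatment period where indicated by" an asterisk, and "Serious TEAEs potentially related to Study Drug" carries one. SAP 3.5.3.2 divides the number of subjects with an event by total patient-years on study.

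In the appendix, Table B1 (LTE Period) has a 60 mg Q12W column, footnoted as serving select analyses. Table B3 (Active Treatment Period) shows the start groups, 115 mg Q12W and Total Active, but no 60 mg Q12W column.

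**The concern.** None of Cohorts A to C received 60 mg Q12W in Part 1. SAP 3.2.2.1 lists their Part 1 groups as 10, 30 and 60 mg Q4W, the first being "10 mg ISIS 814907-treated patients". A column headed 60 mg Q12W that takes in this exposure does not describe its own data.

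Safety is the primary objective. Protocol 2.4.3 gives the aim of Part 2 as evaluating a quarterly interval at two dose levels. The two pooled Q12W columns look like those two levels, and a reader will set them side by side. Only the 115 mg column is true to its heading, because Cohort D received 115 mg Q12W in both parts. A reader of an output table sees the heading and not SAP 3.2.2.2.

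The mismatch with Table B3 is a separate difficulty. Whoever programs the outputs cannot follow both the text and the table.

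**Working it through.** The documents state no person-time share for this group, so there is no planned figure to reproduce. The calculation applies the SAP's own time-on-study rule to the planned design.

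**Inputs**
- Planned cohort sizes: A 8, B 8, C 12, D 16 (protocol 3.1.1).
- Allocation 3:1, giving active + placebo of A 6+2, B 6+2, C 9+3 and D 12+4. Cohorts A to C together: 21+7 = 28.
- Last visits: Day 253 in Part 1 and Day 449 in Part 2 (protocol 3.4), so 253 and 449 days by SAP 3.5.2.
- Doses per patient: 4 in Part 1 for Cohorts A to C, and 5 in Part 2.

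**Person-time in the 60 mg Q12W column, full roll-over**

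Part 1 active: 21 × 253 = 5,313 days. Part 2: 28 × 449 = 12,572 days. Total: 17,885 days.

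| Regimen | Days | Share |
|---|---|---|
| 10 mg Q4W | 6 × 253 = 1,518 | 8.5% |
| 30 mg Q4W | 6 × 253 = 1,518 | 8.5% |
| 60 mg Q4W | 9 × 253 = 2,277 | 12.7% |
| 60 mg Q12W | 12,572 | 70.3% |

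Not 60 mg Q12W: 5,313 / 17,885 = 29.7%.

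**Same check for 115 mg Q12W:** 12 × 253 + 16 × 449 = 10,220 days, all at 115 mg Q12W.

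**By doses:** 21 × 4 = 84 and 28 × 5 = 140, so 84 / 224 = 37.5% are not 60 mg Q12W.

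**By first-to-last-dose duration (SAP 3.5.1):** 21 × 85 / (21 × 85 + 28 × 337) = 1,785 / 11,221 = 15.9%. This is not the rate denominator.

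**Sensitivity to roll-over.** The documents give no expected rate, so r is assumed. Share = 5,313 / (5,313 + r × 12,572).

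| r | Share | Active patients never given 60 mg Q12W, 21 × (1 − r) |
|---|---|---|
| 0.9 | 32.0% | 2.1 |
| 0.8 | 34.6% | 4.2 |
| 0.5 | 45.8% | 10.5 |

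If every patient had the 23-week UK post-treatment period, 7 weeks (49 days) longer than the 16-week one: 5,313 / (5,313 + 28 × 498) = 27.6%.

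**Rate denominator.** As planned: 17,885 / 365.25 = 49.0 patient-years. Part 2 only: 12,572 / 365.25 = 34.4, made up of Late Start A+B+C 8.6, Early Start A 7.4, Early Start B 7.4 and Early Start C 11.1 (rounded).

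**Safety MRI.** SAP 3.5.10 summarises the Active Treatment Period by analysis group at Part 1 Day 169, among other visits. No patient in Cohorts A to C has had 60 mg Q12W by then. On planned numbers the column would hold 6 patients on 10 mg, 6 on 30 mg and 9 on 60 mg, all Q4W.

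**Table B3.** Each Cohort A, B and C row carries two marks (its start group and Total Active). Each Cohort D row carries three (start group, 115 mg Q12W and Total Active). Header and rows agree, so a lost column heading does not explain the gap. Restriction to select analyses does not explain it either, since Table B1 shows its 60 mg column under that same restriction.

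**The case against.** The strongest reply is that nothing is hidden. SAP 3.2.2.2 gives the group a separate definition for each period, so the rule is complete and only a short label is at fault. The column serves select analyses. Early Start A, B and C and Late Start A+B+C are shown separately, MRI summaries name the visit, and no formal test is attached. The Part 2 aim is served by the LTE Period, where the label is right. All of this stands and limits the consequence, but an open definition does not make the heading true.

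On size, 2,277 of the 5,313 days (43%) are Cohort C at 60 mg, the same dose level at a shorter interval, so 17.0% of person-time is at another dose level. That is correct. The 15.9% by dosing duration is also correct, but SAP 3.5.3.2 divides by time on study, so 29.7% is the relevant share.

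On the remedy, a Part 2 rate is not free of earlier exposure: 21 of the 28 planned patients had Q4W dosing in Part 1, and early starters keep their Part 1 baseline (SAP 3.2.3.2). This stands and calls for a footnote.

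On Table B3, the text of its footnote [2] could not be read for this check. A footnote would not supply a column that is absent from the header and all eight rows.

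**Conclusion.** The concern holds and should be fixed before the final analysis. Followed as written, the plan reports patient-year safety rates, including related serious TEAEs, under a regimen that 29.7% of the planned person-time did not receive. That figure assumes planned cohort sizes, full roll-over, complete follow-up and the 16-week Part 2 post-treatment period. Longer UK follow-up lowers it to 27.6% at most; incomplete roll-over raises it.

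The documents give no event risks, so no size or direction of bias in the rate can be stated. The damage is confined to a secondary pooled column, and the components needed for a correct rate are already planned. The disagreement between SAP 3.2.2.2 and Table B3 is a plain inconsistency that has to be settled in any case.

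**What to change.** 1. Rename the Active Treatment Period group in SAP 3.2.2.2, for example Cohorts A–C, any active regimen. Keep the 60 mg Q12W name for the LTE Period group.
2. Add the renamed group to Table B3, with a note that it serves select analyses, as in Table B1.
3. For any rate labelled 60 mg Q12W, use the LTE Period group: subjects with an event in Part 2 per 100 Part 2 patient-years. The counts are planned in SAP 3.5.3.1. For the denominators, SAP 3.5.2 already provides that "Total time on study (patient-years) in each analysis group will be included in the summaries".
4. Footnote that rate to say that 21 of the 28 planned patients had earlier Q4W exposure in Part 1.

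The cost is one label, one table column, one footnote and one rate. No new data are needed, and no dosing or study procedure changes.
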